7.7 EXTENT OF EXPOSURE

Descriptive summary statistics will be produced of the extent of exposure, as defined in [Section 5.4.3](#). A frequency table will also be presented of the extent of exposure by categories (both weekly and 4-weekly categorisations). The total patient-years exposure will also be summarised; the 28-day REP after the last dose of study treatment (see [Section 6.1.6](#)) will not be included for this purpose. These summaries will be produced overall on the TS using both actual maintenance treatment and planned maintenance treatment.

A frequency table will be produced of duration on study (regardless of whether the patient remained on-treatment) using the same 4-weekly categories as extent of exposure.

A descriptive summary and frequency table will be produced of the extent of exposure for patients who discontinued treatment early, using planned maintenance treatment only. This table will be produced in the following 4 ways (using weekly categorisations):

- All patients who prematurely discontinued treatment
- Patients who prematurely discontinued treatment due to AE
- Patients who prematurely discontinued treatment not due to AE
- Patients who prematurely discontinued treatment due to AE and at least one AE with SOC ‘Gastrointestinal disorders’ leading to treatment discontinuation.

7.8 SAFETY ANALYSIS

All safety analyses will be performed on the TS, including only on-treatment data (unless otherwise specified in [Section 7.8.1](#)). No hypothesis testing is planned for safety.

All specified summaries and analysis will be presented for both actual maintenance treatment and planned maintenance treatment.

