**Footnotes for Flow Chart:**

1. Visit 1a is not required if a historical biopsy with sufficient and analysable material was collected within the last 6 months prior to randomisation (refer to [Section 3.3.1](#) and [5.1.1](#)).
2. Day of randomisation and the first administration of trial medication.
3. In case of early discontinuation (ED), Visit 32 should be completed instead of the planned treatment period visit, as soon as possible after trial medication is stopped. Liver biopsy should be performed at the ED visit providing the patient has been on treatment with trial medication for at least 40 weeks. MR imaging does not need to be performed at the ED visit if the patient discontinues before Visit 22 or if another MR imaging was performed within 12 weeks before the ED. [REDACTED] [REDACTED] [REDACTED] [REDACTED] Follow-up Visit 33 should be performed 4 weeks/28 days after the ED visit.
4. Number of weeks since randomization.
5. Trial visits will be conducted in two ways: 1/ at site (indicated by “S” in the [Flow Chart](#)) and 2/ remotely via telemedicine from patient’s home (indicated by “T” in the Flow Chart). Method of visit conduct (on-site or remote) can be modified. Modifications from an on-site to a remote visit require Sponsor approval.
6. Visit 1 can be conducted within less than 10 weeks of randomization. Before randomization, the Investigator should ensure that all safety laboratory results, ECG reading, imaging and liver biopsy results are available to ensure that the patient meets all inclusion criteria and does not meet any exclusion criteria. In the event of logistical issues with the reporting of results by the central vendor(s) a patient who meets all inclusion criteria and does not meet any exclusion criteria should be considered for participation in the clinical trial even if he/ she exceeds the screening period of 10 weeks. Extension of the screening period requires a Sponsor approval. If more than 12 weeks elapse from Visit 1 safety laboratory tests, ECG and vital signs should be repeated and results should be available before randomization.
7. Patient must be informed and written informed consent must be obtained prior to starting any trial procedure. Fasting is considered part of a trial procedure. For the historical biopsy, if applicable, a written non-trial specific informed consent has been obtained (per local standard).
8. Physical examination after screening is required only if patient reports symptoms.

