### 4.3 TREATMENT COMPLIANCE

Patients should be encouraged to be fully compliant with the trial medication dosing schedule ([Flow Chart](#)).

If a dose is missed on the planned dosing day, patients should take the planned dose within two days. If more time has elapsed since the missed dose, then the patients should wait to take the next planned dose. A minimum of five days between doses is required.

Patients are considered out of compliance, and should be discontinued from the trial:

- 1) if they miss two or more consecutive doses OR if they miss one dose at more than two occasions during dose escalation period;
- 2) if they miss three or more consecutive doses OR if they miss one dose or two consecutive doses at more than two occasions during maintenance period.

The total maximum number of allowable missed doses during the entire treatment period is six, i.e., two during the dose escalation and four during the maintenance period.

Patients should be instructed to return all unused trial medication (cartons with the pre-filled syringes), and the empty cartons from used trial medication, to the site at the next site visit. Compliance will be determined by the site personnel.

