### **6.2.2 Treatment period(s)**

Patients who meet all eligibility criteria will be randomised at Visit 2. After randomization, patients will start the treatment period which includes a dose escalation, followed by the maintenance period as shown in [Figure 3.1: 1](#).

Unscheduled visits may be arranged if necessary. Procedures completed during an unscheduled visit will depend on the circumstances under which the visit was planned, and at the discretion of the Investigator.

Measurement of vital signs should be performed before blood samples are taken (pre-dose) and approx. 10 minutes after dosing (post-dose).

Data concerning adverse events and concomitant medications will be collected throughout the trial, as specified in the [Flow Chart](#). These data will be obtained at scheduled or

unscheduled visits based on the information provided actively by the patient or as a result of questioning the patient.

After completion of the treatment period or after a premature trial discontinuation, patient will have the End of Treatment visit (Visit 32) and will be registered as completed or discontinued in IRT, as applicable. Trial medication will not be administered at Visit 32, the last administration of the trial medication will occur one week before the visit.

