### 7.2.5 Safety analyses

Adverse events will be coded using the Medical Dictionary for Drug Regulatory Activities (MedDRA). Standard BI summary tables and listings will be produced. All adverse events with an onset between start of treatment and end of the residual effect period (REP), a period of 28 days after the last dose of trial medication, will be assigned to the on-treatment period for evaluation.

Safety analyses will be performed on the TS, using the actual maintenance treatment received. Key safety analyses will also be performed using the randomised maintenance treatment (if this is different for any patient).

In general, safety analyses will be descriptive in nature and will be based on BI standards. No hypothesis testing is planned.

Statistical analysis and reporting of adverse events will concentrate on treatment-emergent adverse events, i.e., all adverse events occurring between start of treatment and end of the REP.

Frequency, severity, and causal relationship of adverse events will be tabulated by system organ class and preferred term after coding according to the current version of the Medical Dictionary for Drug Regulatory Activities (MedDRA) at database lock.

The adjudicated events will be summarised descriptively for each treatment group.

Laboratory data will be analysed both quantitatively as well as qualitatively. The latter will be done via comparison of laboratory data to their reference ranges. Values outside the reference range as well as values defined as clinically relevant will be summarised. Treatment groups will be compared descriptively with regard to distribution parameters as well as with regard to frequency and percentage of patients with abnormal values or clinically relevant abnormal values.

Vital signs, physical examinations and 12-lead ECG observed at screening, baseline, during the course of the trial and at the end-of-trial evaluation will be assessed with regard to possible changes compared to findings before start of treatment.

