6.1.6 Definition of On-Treatment

There is no continued study participation for patients who have discontinued treatment early. Consequently off-treatment data capture is expected to be restricted to those data captured during the safety follow-up period specified by the CTP, although there may be occasional unplanned exceptions to this.

Even for patients who completed treatment according to the protocol, data captured during the follow-up period may be relevant for safety.

It is important to be clear whether all available data will be used in a particular summary or analysis, or whether only on-treatment data will be used. The definition of “on-treatment” for this purpose is as described below, and it includes any temporary treatment interruptions which might occur prior to last dose of study treatment. It is assumed that all patients will have a date of last administration of study medication accurately recorded on the End of Treatment eCRF page.

“Off-treatment” refers to data which are captured after baseline but which are not “on-treatment” as defined below.

Safety

An AE start date or other safety assessment date will be considered “on-treatment” if the AE start date or assessment date is between the date of first dose and 28 days after the date of last

dose of study treatment inclusive (the residual effect period (REP) is defined as 28 days in this trial).

The same on-treatment definition will be used for all types of safety data.

Efficacy

All post-baseline efficacy data (including for exploratory biomarkers) will use the same 28-day definition of “on-treatment” as for safety, where on-treatment analyses are specified (as opposed to those efficacy analyses which use all data, both on- and off-treatment).

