Any vital signs record for which no time of study drug administration exists (expected to include measurements recorded during the 28 day REP and scheduled Week 48 measurements) will be considered “pre-dose” according to the above rules. Only pre-dose measurements will be used for efficacy purposes (blood pressure further endpoints).

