7.8.1 Adverse Events

The analyses of adverse events will be descriptive in nature. All analyses of AEs will be based on the number of patients with AEs and not on the number of AEs.

The analysis of adverse events will be based on the concept of treatment emergent adverse events. AEs will be considered “on-treatment” if the AE start date meets the 28-day REP criterion (see [Section 6.1.6](#)). AEs occurring prior to the start of treatment will be assigned to “screening”. AEs occurring more than 28 days after the last dose of study treatment will be assigned to “follow-up”. Unless otherwise specified, on-treatment AEs will be pooled across dose escalation and maintenance periods.

An overall summary of adverse events will be presented for all patients in the TS. This summary will show the number and percent of patients with any AE, any investigator defined drug-related AE, any AE leading to the discontinuation of study medication, any AESI (as determined by the investigator), any serious AE (including reason for serious (death, life-threatening, disability/permanent damage, required or prolonged hospitalization, congenital anomaly/birth defect and other medically important events)), and any drug-related serious AE. The overall summary will be presented with the treatment period pooled across, and split into, dose escalation and maintenance periods, respectively.

AEs will be coded using the version of the MedDRA coding dictionary in force at final DBL. The frequency of patients with all AEs will be summarised by treatment, primary system organ class (SOC) and preferred term (PT). A patient with multiple on-treatment occurrences of the same preferred term meeting the criteria for inclusion in the table will be counted only once in these tabulations. SOC's will be sorted by descending overall frequency; PT's will be sorted by descending overall frequency (within SOC). The summary of all AEs will be presented with the treatment period pooled across, and split into, dose escalation and maintenance periods, respectively.

The AE summary by primary SOC and PT will also be repeated for each of the following, with the treatment period pooled across dose escalation and maintenance periods, only:

- AEs leading to treatment discontinuation
- Serious AEs
- Investigator-defined drug-related AEs
- Drug-related serious AEs.

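### Visit 33 falls after the 28-day on-treatment cut-off for every completer seen in window, so its laboratory, vital-sign and C-SSRS data enter no specified safety summary

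*SAP*

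**What the plan says.** **Schedule.** Protocol 6.2.2 gives no dose at Visit 32 and says that "the last administration of the trial medication will occur one week before the visit". The Flow Chart puts Visit 32 at Day 337 (±2 days) and Visit 33 at 28 days after it (+5 days). For early discontinuers, Flow Chart footnote 3 says "Follow-up Visit 33 should be performed 4 weeks/28 days after the ED visit". Safety laboratory tests, vital signs and the C-SSRS are scheduled at Visit 33; the 12-lead ECG is not.

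**Cut-off.** SAP 6.1.6 ends the on-treatment period 28 days after the last dose, inclusive. The protocol sets the same limit in 7.2.1 and 7.2.5.

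**Use of data.** SAP 7.8: "All safety analyses will be performed on the TS, including only on-treatment data". The sentence goes on to allow exceptions made in SAP 7.8.1. SAP 6.7 settles on-treatment status before it assigns visit windows. Table 6.7:1 ends with an open Week 48 window (Day 323 onward) and has no follow-up row. SAP 7.8.2 shows laboratory values by scheduled week, plus the on-treatment last, minimum and maximum. SAP 7.8.3 and 7.8.5 (vital signs, C-SSRS) state no exception.

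**Adverse events.** SAP 7.8.1 classifies by start date. "AEs occurring more than 28 days after the last dose of study treatment will be assigned to" a follow-up category, for which no table is named.

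**Signs of intent.** SAP 6.1.6 accepts that, even for completers, "data captured during the follow-up period may be relevant for safety". For vital-sign records with no dosing time, SAP 6.7 says these are "expected to include measurements recorded during the 28 day REP", and names the Week 48 measurements separately.

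**The concern.** The cut-off is counted from the last dose, but the follow-up visit is counted from Visit 32, a week later. A 28-day follow-up visit and a 28-day residual effect period look matched but are not. The one scheduled visit after treatment lands outside the only period that the safety summaries use.

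Three things are at stake:

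- No specified table can show whether pulse, lipase or ALT move back after the drug is stopped.
- After Visit 1 the C-SSRS asks about the time since the last visit. The Visit 33 form is therefore the only scheduled form covering most of the residual effect period, yet it is left out because of the date on which it was completed.
- Hepatic injury is the only pre-specified adverse event of special interest. The liver table in SAP 7.8.2 looks for raised bilirubin or INR up to 30 days after an ALT or AST rise. For a rise at Visit 32 that can reach Visit 33, and the SAP does not say which rule then prevails.

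**Working it through.** **Inputs.** Day = 7 × week + 1, which reproduces the Flow Chart's Day 337 for Week 48. The last dose is at Week 47: 7 × 47 + 1 = Day 330. Protocol 4.3 allows lateness ("patients should take the planned dose within two days"), so the latest last dose is Day 332. The cut-off is last dose + 28. Visit 33 is Visit 32 + 28 to + 33.

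**The protocol's own statement.** Protocol 6.2.3 says that the interval from last dose to end of follow-up covers the 28-day residual effect period. Nominally 365 − 330 = 35 days, so this is correct. It also means that the visit itself comes after the period has ended.

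**Completers.**

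| Case | Last dose | On-treatment ends | Visit 32 | Visit 33 | Days after last dose | Days past cut-off |
|---|---|---|---|---|---|---|
| Shortest gap | 332 | 360 | 335 | 363 | 31 | 3 |
| Nominal | 330 | 358 | 337 | 365 | 35 | 7 |
| Longest gap | 330 | 358 | 339 | 372 | 42 | 14 |

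All allowed combinations were enumerated: 3 dose days × 5 Visit 32 days × 6 Visit 33 days × 2 ways of counting (from the actual or the planned Visit 32) = 180. The gap runs from 31 to 42 days, and none is 28 or less. For the earliest possible Visit 33 (Day 363) to count, the last dose would have to be on Day 363 − 28 = 335, five days late against an allowance of two.

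**Early discontinuers.** If the early-discontinuation visit is d days after the last dose, Visit 33 is at d + 28 to d + 33. It counts only if d = 0 and the visit is held exactly 28 days later.

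**Other routes into the tables.** Day 365 would fit the open Week 48 window, but the on-treatment filter is applied first. SAP 6.7 derives last, minimum and maximum values without regard to window selection, but SAP 7.8.2 limits them to on-treatment values.

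**C-SSRS.** Nominally Visit 32 is day 337 − 330 = 7 after the last dose. The Visit 33 form therefore covers days 7 to 35, of which 28 − 7 = 21 days lie inside the 28-day residual effect period.

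**Liver table.** For an ALT or AST rise at Day 337, the look-ahead runs to 337 + 30 = Day 367. Nominal Visit 33 (Day 365) lies within it, but after the on-treatment limit (Day 358). Visit 33 can be used if held 28 to 30 days after Visit 32, but not at 31 to 33 days.

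**Adverse events.** Of the nominal 28 days from Visit 32 to Visit 33, the first 358 − 337 = 21 are on-treatment and the last 7 are not. Across the windows the uncovered stretch is 3 to 14 days.

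**The case against.** The strongest case against is that adverse events, the core of the safety evaluation, are largely protected. That stands, in these parts:

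- **Exception clause.** The SAP 7.8 sentence defers to 7.8.1, which governs adverse events and adjudicated events.
- **Start-date rule.** An event starting by day 28 is tabulated even if first reported at Visit 33. So is an event that began on-treatment and later proved fatal.
- **Serious C-SSRS findings.** Protocol 5.2.5.1 requires type 4 or 5 ideation and all suicidal behaviour to be reported as SAEs, so they reach the adverse-event tables by onset date. Ideation of types 1 to 3 does so only if the investigator judges it an adverse event.
- **COVID-19 tables.** These are in SAP 7.9, outside the 7.8 rule.

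A reader might infer that late deaths or neoplasms appear in no safety table. The documents do not support this. The adjudicated-event paragraph sets no time limit; the 7.8 default would restrict it, but the SAP does not say so. Its scope is unclear, which is not a stated exclusion.

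A reader might also infer that SAP and protocol conflict. On the cut-off they agree. Protocol 7.2.5 does say that vital signs, physical examinations and ECG "during the course of the trial and at the end-of-trial evaluation will be assessed with regard to possible changes", but ECG is not scheduled at Visit 33, so the evaluation meant may be Visit 32. Likewise, the vital signs that SAP 6.7 expects in the residual effect period could come from early-discontinuation or unscheduled visits. Both passages are weak support.

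Finally, sponsor-standard listings and redacted text may show Visit 33 data. What can be said is that no summary is specified, not that the data vanish. Safety is descriptive and off-drug recovery is not a main objective, which limits the weight but does not explain collecting the data without a planned summary.

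**Conclusion.** The point holds for measurements taken at Visit 33. Every completer seen within the allowed windows has that visit 31 to 42 days after the last dose (nominally 35), and SAP 6.7 and 7.8 together keep its laboratory, vital-sign and C-SSRS values out of every specified safety summary. The same applies to early discontinuers, except where the discontinuation visit is on the last-dose day and Visit 33 exactly 28 days later.

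For adverse events it is a small gap: onsets after day 28, about 3 to 14 days of follow-up (nominally 7), are given a category without a table. Whether the adjudicated-event table includes such late events needs to be stated.

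This rests on the last dose being taken at Week 47 no more than two days late. A missed final dose would lengthen the gap. It also rests on the text that can be read. The 28-day rule itself is not at fault. This is a worthwhile, low-cost correction and does not affect the efficacy conclusions.

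**What to change.** Keep the 28-day rule for the treatment-emergent tables, and change the SAP as follows:

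1. In 6.7, 7.8.2, 7.8.3 and 7.8.5, add a Follow-up (Visit 33) time point for laboratory, vital-sign and C-SSRS tables, assigned by nominal visit and using both on- and off-treatment data.
2. In 7.8.2, state that the 30-day bilirubin/INR look-ahead may use Visit 33 values.
3. In 7.8.1, add one table of AEs, SAEs and deaths with onset more than 28 days after the last dose.
4. In 7.8.1, present adjudicated events twice: on-treatment and over the whole study.

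The cost is SAP wording and a few extra descriptive tables from data already collected. No visit or procedure changes.

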7.8.1 Adverse Events

The analyses of adverse events will be descriptive in nature. All analyses of AEs will be based on the number of patients with AEs and not on the number of AEs.

The analysis of adverse events will be based on the concept of treatment emergent adverse events. AEs will be considered “on-treatment” if the AE start date meets the 28-day REP criterion (see [Section 6.1.6](#)). AEs occurring prior to the start of treatment will be assigned to “screening”. AEs occurring more than 28 days after the last dose of study treatment will be assigned to “follow-up”. Unless otherwise specified, on-treatment AEs will be pooled across dose escalation and maintenance periods.

An overall summary of adverse events will be presented for all patients in the TS. This summary will show the number and percent of patients with any AE, any investigator defined drug-related AE, any AE leading to the discontinuation of study medication, any AESI (as determined by the investigator), any serious AE (including reason for serious (death, life-threatening, disability/permanent damage, required or prolonged hospitalization, congenital anomaly/birth defect and other medically important events)), and any drug-related serious AE. The overall summary will be presented with the treatment period pooled across, and split into, dose escalation and maintenance periods, respectively.

AEs will be coded using the version of the MedDRA coding dictionary in force at final DBL. The frequency of patients with all AEs will be summarised by treatment, primary system organ class (SOC) and preferred term (PT). A patient with multiple on-treatment occurrences of the same preferred term meeting the criteria for inclusion in the table will be counted only once in these tabulations. SOC's will be sorted by descending overall frequency; PT's will be sorted by descending overall frequency (within SOC). The summary of all AEs will be presented with the treatment period pooled across, and split into, dose escalation and maintenance periods, respectively.

The AE summary by primary SOC and PT will also be repeated for each of the following, with the treatment period pooled across dose escalation and maintenance periods, only:

- AEs leading to treatment discontinuation
- Serious AEs
- Investigator-defined drug-related AEs
- Drug-related serious AEs.

An additional table will present the frequency of patients with AEs by worst CTCAE grade (1 to 5) and by primary SOC and PT. When no events meet the criteria for inclusion, the table will be shown as indicating no events of that type have occurred.

The following tables will be produced separately by baseline body weight subgroup (< 100 / ≥ 100 kg) and by presence of diabetes (yes/no):

- Overall AE summary
- Summary of all AEs by primary SOC and PT
- Summary of AEs leading to treatment discontinuation by primary SOC and PT.

For disclosure of AE data on ClinicalTrials.gov, the frequency of patients with non-serious AEs occurring with an incidence of greater than 5% (PT occurring in more than 5% of treated patients in one or more treatment groups) will be summarised by treatment, primary SOC and PT. The frequency of patients with serious AEs and drug related serious AEs will also be summarised respectively.

For disclosure of AE data in the EudraCT register, the frequency of patients with AEs, the frequency of patients with non-serious AEs with an incidence of greater than 5% (as above) and the frequency of patients with serious AEs will be summarised. Furthermore, the total number of treated patients by country and by age group will be summarised.

An exposure-adjusted summary of all AEs by primary SOC and PT will also be produced. For this purpose, the time at risk will be defined for specific AEs as follows:

- For patients with no events, the time at risk is the number of days on-treatment (inclusive), as defined in [Section 6.1.6](#)
- For patients with one or more event, the time at risk is the number of days from the start of treatment to the start of the first on-treatment event (inclusive).

The total time at risk (years) for a treatment group is the sum of the individual patient times at risk for that treatment group (days) divided by 365.25. Multiple occurrences of the same event for a particular patient will not be counted as separate events in this summary; a patient will either be considered to have no events of the type being summarised, or to have one or more occurrences of that event.

A frequency table will be produced of symptoms of injection site reaction (swelling, induration, heat, redness, pain, other) for the subset of patients with the event.

Additional trial-specific information captured in the eCRF for Grade 3 nausea will be listed only and not summarised.

Adverse Events of Special Interest (AESIs)

Hepatic injury is the only AESI pre-specified in the CTP. No further AESIs have been identified through increasing knowledge of the drug safety profile during the conduct of the trial.

AESIs as recorded by the investigator on the eCRF page will be summarised as part of the overall AE summary, described above.

Investigator-recorded AESIs will also be summarised by treatment, primary SOC and PT.

An additional table will present the frequency of patients with AEs possibly indicating hepatic injury, as defined by the four MedDRA subSMQ definitions given below:

- Liver related investigations, signs and symptoms (narrow subSMQ)
- Cholestasis and jaundice of hepatic origin (narrow subSMQ)
- Hepatitis, non-infectious (narrow subSMQ)

- Hepatic failure, fibrosis and cirrhosis and other liver damage-related conditions (narrow subSMQ).

This table will be summarised by treatment, MedDRA subSMQ, primary system organ class and preferred term. Any preferred term which is classified under more than one subSMQ will be included under each relevant subSMQ.

Adjudicated Adverse Events

The number and percent of patients with each of the following confirmed adjudicated events (as defined in the CTP) will be presented:

- All-cause death
- Cardiovascular event
- Cerebrovascular disease
- Heart failure requiring hospitalisation
- Pancreatitis
- Neoplasm
- Thyroid mass requiring surgery.

It should be noted that “Heart failure requiring hospitalisation” is assessed by the same committee who are adjudicating cardiovascular events, and is recorded on the same form as all of the other cardiovascular event sub-categories (which were not distinguished in the same way in the CTP). Therefore the summary table will reflect the data actually captured.

